5.2 Subject Selection

Written informed consent must be obtained prior to the subject undergoing any study-related procedure, including screening tests. All subjects will be required to fulfill the entry criteria listed below

Inclusion Criteria

Subjects who meet all of the following criteria are eligible for enrollment into the study:

1. Subject is capable of providing written informed consent
2. Subject is ≥ 18 years old and ≤ 65 years old
3. Meets at least 4 of 11 modified American College of Rheumatology (ACR) (1997) Revised Criteria for the Classification of Systemic Lupus Erythematosus
4. Has mild to moderate disease activity defined as
 - A minimum SLEDAI score of 2 excluding points for serology (anti-dsDNA antibody and complement)
 - No active renal or nervous system disease
 - No BILAG A in any organ system
 - No expectation by the investigator that corticosteroids will need to be added or doses increased during the 8 week treatment period for any reason
 - No expectation by the investigator that immunosuppressive medication will need to be added or doses increased during the 8 week treatment period
5. Has elevated titers of anti-ds DNA antibody at the time of screening (defined as the titer that meets criteria for “high” in the Core Laboratory at the North Shore/LIJ Health Systems; unequivocal high titer as opposed to borderline, indeterminate or intermediate).
6. Has elevated titers of cross-reactive anti-DNA/DWEYS antibodies at the time of screening (the assays for anti-DNA/DWEYS antibodies will be performed in Dr. [name]’s laboratory; study sites will be notified of results within 3 days of receipt of the samples).
7. If on glucocorticoids, the dose must be ≤ 10 mg daily and stable or decreasing 4 weeks prior to baseline
8. If on immunosuppressive or immunomodulatory medication such as azathioprine, methotrexate, leflunomide, mycophenolate, belimumab or hydroxychloroquine, the dose must have been stable for the 3 months prior to screening, and expected to remain stable over the course of the study.
9. Males and females with potential for reproduction must agree to practice effective birth control measures (2 approved methods of contraception). Nelfinavir can decrease serum levels of oral contraceptives; the slightly increased risk of pregnancy due to an interaction between oral contraception and nelfinavir will be discussed when appropriate and the requirement for a second approved method of contraception will be addressed.

Exclusion Criteria

Subjects who meet any of the following criteria are disqualified from enrollment in the study:

1. Current or prior treatment with rituximab or anti-CD22 monoclonal antibody in the 12 months prior to this study or any other biologic agent for 90 days prior to this study
2. Treatment with cyclophosphamide within the 6 months prior to screening
3. Increase in glucocorticoid dose within 4 weeks of screening or addition of a DMARD in the three months prior to study
4. A history of drug or alcohol abuse within the 6 months prior to screening
5. Elevated LFT's:
 - ALT or AST ≥ 2 x upper limit of normal at screening
 - serum unconjugated bilirubin > 3 mg/dL at screening
6. Dialysis or serum creatinine >1.5 mg/dL
7. Hypercholesterolemia: total cholesterol >230 mg/dL or LDL >150 mg/dl or hypertriglyceridemia (triglyceride >200 mg/dL) at screening
8. Laboratory/clinical evidence of: pancreatitis: amylase/lipase >3 x upper limit of normal at screening
9. Known current/active infections including HIV, Hepatitis B, Hepatitis C
10. History of cancer, excluding skin cancers (squamous cell or basal cell that have been treated)
11. Known active tuberculosis or untreated tuberculosis
12. Hemoglobin < 8 g/dL
13. Expectation by the investigator to increase corticosteroid or immunosuppressive, or immunomodulatory medication dose at screening, baseline, or over the course of the study
14. Pregnancy or lactation
15. Consumption of > 2 cups of grapefruit juice per day
16. Treatment with medications metabolized using the cytochrome P3A4 pathway, such as cyclosporine, tacrolimus, gemfibrozil, niacin, itraconazole, ketoconazole, erythromycin, azithromycin, clarithromycin, bosentan, nefazodone, tricyclic antidepressants
17. Treatment with any drugs known to interact with nelfinavir that include amiodarone, quinidine, midazolam, triazolam, ergotamine, dihydroergotamine, methylergonovine, pimozide, lovastatin, simvastatin, rifampin, St. John's Wort, aluzosin, cisapride and sildenafil.
18. Any condition that, in the opinion of the Investigator, would jeopardize the subject's safety following exposure to the study drug.

5.3 Concomitant medications

Use of corticosteroids, immunosuppressive or immunomodulatory medications are allowed per inclusion and exclusion criteria. Doses of these agents must remain stable throughout the study period. NSAIDS and Tylenol are allowed but should be held overnight or for 12 hours prior to each assessment of disease activity on Days 1, 28, 56 and 84. Subjects will be asked not to start new over the counter medications, nutritional supplements or vitamins during the course of the study.

Use of increased or added doses of corticosteroids for purposes other than SLE treatment are discouraged, however, in the event of medical necessity can be allowed in the following circumstances:

- Daily doses up to a maximum of 30 mg per day will be allowed for a maximum of 2 days if the last dose is taken more than 5 days from the day 56 assessment.

5.4 Study Procedures

(Note: see **MOOP Figure 1** for a Schedule of Events that lists all study procedures)

All study information will be collected on Case Report Forms (CRFs) that will be scanned and emailed to the Central Study Coordinator (CSC) at the FIMR within 7 days of each study visit. For sites that do not have secure encrypted email, the CRFs will be transmitted via a secure fax to the CSC at the FIMR. A dedicated data transfer technician will be responsible for transferring data from the CRFs to the secure database in the Biostatistics Unit at the FIMR.

5.4.1 Study Visits

Screening Visit: Each potential participant will provide written informed consent and no study procedures will be done prior to this. Consenting subjects will participate in a screening visit where assessments will be performed to establish eligibility. The screening visit will include assessments of the following:

- Demographic data
- Medical history, including American College of Rheumatology criteria for SLE
- Physical exam
- Medication review
- Tuberculosis exposure*
- Laboratory assessments:
 - **Central Laboratory:** Serum to be sent overnight to the Coordinating Center at the FIMR. The CSC will be responsible for sending de-identified samples to the [name] Laboratory at the FIMR for anti-DNA/DWEYS antibody testing and to the Core Laboratory in the North Shore LIJ Health System for anti-dsDNA antibody testing. Results will be available to the participating sites within 3 days of receipt at the FIMR. See **MOOP Appendix E** for processing, storing and shipping details.
 - **Local Laboratory** (at the participating site):
 - CBC with differential
 - Comprehensive chemistry
 - C3, C4
 - Urinalysis with micro
 - HIV, Hepatitis B, Hepatitis C
 - Serum β HCG for women of childbearing potential
 - Subjects will be asked to return for a fasting lipid profile
- Disease activity assessments:
 - SELENA SLEDAI
 - BILAG

*All subjects will be tested for latent infection with mycobacterium tuberculosis using the purified protein derivative (PPD) skin test or the Quantiferon Gold test unless 1) they have a history of a positive PPD and have undergone treatment or 2) they have documentation of a negative TB test (PPD or Quantiferon Gold) within the preceding 3 months from screening. PPD will be administered subcutaneously and subjects will be asked to return for the PPD reading in 48-72 hours as per PPD guidelines. If preferred, the Quantiferon Gold test can be sent instead of the PPD. All subjects with a positive PPD or Quantiferon Gold test that have not previously received a full course of treatment are excluded from this study (see exclusion criteria). If a subject has received the BCG vaccine and the PPD test is equivocal, the investigator may choose to use the quantiferon gold test. Subjects with positive PPD or quantiferon gold tests who have not previously been treated for TB will be referred for further evaluation (e.g. including chest X-ray and sputum culture and smear).

Day 1 (initiation of treatment):

NSAIDS and Tylenol should be held overnight or for 12 hours prior to the assessments on Day 1. The following assessments will take place on Day 1 prior to dosing with the study medication for those subjects who meet eligibility criteria *and are returning for the Day 1 visit more than 10 days after the screening visit:*

- Medical history
- Adverse event review
- Physical exam
- Medication review
- For women of childbearing potential a urine pregnancy test must be negative prior to dosing with study medication
- Laboratory assessments prior to dosing with study medication
 - **Local Laboratory** (at the participating site)
 - CBC with differential
 - Comprehensive chemistry, amylase, lipase
 - C3, C4
 - Urinalysis with micro
 - **Central Laboratory** (see **MOOP Appendix E** for processing, storage and shipping instructions)
 - anti-dsDNA and anti-DNA/DWEYS antibody titers,
 - antibodies to Sm, RNP, Ro, La, anticardiolipin antibodies: IgG, IgA, IgM
 - cytokine levels
 - interferon signature
 - CRP
- Disease activity assessments:
 - SELENA SLEDAI
 - BILAG
 - Joint count
 - PGA
 - SLICC Damage Index
- Patient Assessments:
 - LupusPRO
 - Patient global assessment (PtGA)

- Dispense 30 days of study drug, nelfinavir

For subjects that meet eligibility criteria returning for the Day 1 visit *within 10 days of the screening visit*, the SELENA SLEDAI assessment obtained at screening should be used as the Day 1 SELENA SLEDAI and a repeat CBC, comprehensive chemistry, C3, C4 and urinalysis with micro will not be performed. The following assessments will be performed for these subjects at the Day 1 visit prior to dosing with the study medication:

- Medical history
- Adverse event review
- Physical exam
- Medication review
- For women of childbearing potential a urine pregnancy test must be negative prior to dosing with study medication
- Disease activity assessments:
 - BILAG
 - Joint count
 - PGA
 - SLICC Damage Index
- Patient Assessments:
 - LupusPRO
 - Patient global assessment (PtGA)
- Laboratory assessments prior to dosing with study medication
 - **Central Laboratory** (see MOOP Appendix E for processing, storage and shipping instructions)
 - anti-dsDNA and anti-DNA/DWEYS antibody titers,
 - antibodies to Sm, RNP, Ro, La, anticardiolipin antibodies: IgG, IgA, IgM
 - cytokine levels
 - interferon signature
 - CRP
- Dispense 30 days of study drug, nelfinavir

Day 7: All subjects will return on Day 7 for the following assessments:

- Medical history, including assessment of nelfinavir tolerability
- Adverse event review
- Physical exam
- Medication review (including a pill count for study drug; nelfinavir)
- Hyperglycemia assessment: Subjects will be asked about symptoms of hyperglycemia: increased thirst, increased hunger, frequent urination and weight loss. If symptoms are present, a serum glucose (using a fingerstick measurement or a chem-7 measurement) should be obtained. Based on the serum glucose level, the following guidelines should be followed:
 - Grade 1 or 2 Hyperglycemia (serum glucose < 250)
 - In subjects with pre-existing diabetes: these subjects can be allowed to continue in the study with intensification of their diabetes regimen and glucose monitoring

- In subjects with no history of hyperglycemia or diagnosis of diabetes: these subjects should be taken off the study medication and discontinued from the study (section 6.1.1).
- Grade 3 hyperglycemia (serum glucose > 250): subjects should be taken off study medication, discontinued from the study (section 6.1.1), treated and followed for resolution of the hyperglycemia.

Day 14: Subjects will be asked to fast after midnight the night prior to this visit. All subjects will return on Day 14 for the following assessments:

- Medical history, including assessment of nelfinavir tolerability
- Adverse event review
- Physical exam
- Medication review (including a pill count for study drug; nelfinavir)
- Hyperglycemia assessment: Subjects will be asked about symptoms of hyperglycemia: increased thirst, increased hunger, frequent urination and weight loss. If symptoms are present, a serum glucose (using a fingerstick measurement or a chem-7 measurement) should be obtained. Based on the serum glucose level, the following guidelines should be followed:
 - Grade 1 or 2 Hyperglycemia (serum glucose < 250)
 - In subjects with pre-existing diabetes: these subjects can be allowed to continue in the study with intensification of their diabetes regimen and glucose monitoring
 - In subjects with no history of hyperglycemia or diagnosis of diabetes: these subjects should be taken off the study medication and discontinued from the study (section 6.1.1).
 - Grade 3 hyperglycemia (serum glucose > 250): subjects should be taken off study medication, discontinued from the study (section 6.1.1), treated and followed for resolution of the hyperglycemia.
- Laboratory assessments
 - **Local Laboratory** (at the participating site)
 - CBC with differential
 - Comprehensive chemistry, amylase, lipase
 - Urinalysis with micro
 - Fasting lipid profile
 - **Central Laboratory** (see **MOOP Appendix E** for processing, storage and shipping instructions)
 - anti-dsDNA and anti-DNA/DWEYS antibody titers,
 - antibodies to Sm, RNP, Ro, La, anticardiolipin antibodies: IgG, IgA, IgM
 - cytokine levels
 - interferon signature
 - CRP

Day 28: Subjects will be asked to refrain from taking Tylenol or NSAIDS and to fast after midnight the night prior to this visit. All subjects will return on Day 28 for the following assessments:

- Medical history, including assessment of nelfinavir tolerability
- Adverse event review
- Physical exam
- Medication review (including a pill count for study drug; nelfinavir)
- For women of childbearing potential a urine pregnancy test must be negative prior to continued dosing with study medication
- Hyperglycemia assessment: Subjects will be asked about symptoms of hyperglycemia: increased thirst, increased hunger, frequent urination and weight loss. If symptoms are present, a serum glucose (using a fingerstick measurement or a chem-7 measurement) should be obtained. Based on the serum glucose level, the following guidelines should be followed:
 - Grade 1 or 2 Hyperglycemia (serum glucose < 250)
 - In subjects with pre-existing diabetes: these subjects can be allowed to continue in the study with intensification of their diabetes regimen and glucose monitoring
 - In subjects with no history of hyperglycemia or diagnosis of diabetes: these subjects should be taken off the study medication and discontinued from the study (section 6.1.1).
 - Grade 3 hyperglycemia (serum glucose > 250): subjects should be taken off study medication, discontinued from the study (section 6.1.1), treated and followed for resolution of the hyperglycemia.
- Disease activity assessments:
 - SELENA SLEDAI
 - BILAG
 - Joint count
 - PGA
- Patient Assessments:
 - LupusPRO
 - Patient global assessment (PtGA)
 - **Local Laboratory** (at the participating site)
 - CBC with differential
 - Comprehensive chemistry, amylase, lipase
 - C3, C4
 - Fasting lipid profile
 - Urinalysis with micro
 - **Central Laboratory** (see **MOOP Appendix E** for processing, storage and shipping instructions)
 - anti-dsDNA and anti-DNA/DWEYS antibody titers,
 - antibodies to Sm, RNP, Ro, La, anticardiolipin antibodies: IgG, IgA, IgM
 - cytokine levels
 - interferon signature
 - CRP
- Dispense 30 days of study drug, nelfinavir

Day 56 (last day of study drug): Subjects will be asked to refrain from taking Tylenol or NSAIDS and to fast after midnight the night prior to this visit. Subjects will return on Day 56 for the following assessments:

- Medical history, including assessment of nelfinavir tolerability
- Adverse event review
- Physical exam
- Medication review (including a pill count for study drug; nelfinavir)
- For women of childbearing potential a urine pregnancy test will be done
- Hyperglycemia assessment: Subjects will be asked about symptoms of hyperglycemia: increased thirst, increased hunger, frequent urination and weight loss. If symptoms are present, a serum glucose (using a fingerstick measurement or a chem-7 measurement) should be obtained. Based on the serum glucose level, the following guidelines should be followed:
 - Grade 1 or 2 Hyperglycemia (serum glucose < 250)
 - In subjects with pre-existing diabetes: these subjects can be allowed to continue in the study with intensification of their diabetes regimen and glucose monitoring
 - In subjects with no history of hyperglycemia or diagnosis of diabetes: these subjects should be taken off the study medication and discontinued from the study (section 6.1.1).
 - Grade 3 hyperglycemia (serum glucose > 250): subjects should be taken off study medication, discontinued from the study (section 6.1.1), treated and followed for resolution of the hyperglycemia.
- Disease activity assessments:
 - SELENA SLEDAI
 - BILAG
 - Joint count
 - PGA
- Patient Assessments:
 - LupusPRO
 - Patient global assessment (PtGA)
 - **Local Laboratory** (at the participating site)
 - CBC with differential
 - Comprehensive chemistry, amylase, lipase
 - C3, C4
 - Fasting lipid profile
 - Urinalysis with micro
 - **Central Laboratory** (see **MOOP Appendix E** for processing, storage and shipping instructions)
 - anti-dsDNA and anti-DNA/DWEYS antibody titers,
 - antibodies to Sm, RNP, Ro, La, anticardiolipin antibodies: IgG, IgA, IgM
 - cytokine levels
 - interferon signature

- CRP

Day 84 (end of study): Subjects will be asked to refrain from taking Tylenol or NSAIDS after midnight the night prior to this visit. Subjects will return on Day 84 for the following assessments:

- Medical history
- Adverse event review
- Physical exam
- Hyperglycemia assessment: Subjects will be asked about symptoms of hyperglycemia: increased thirst, increased hunger, frequent urination and weight loss.
- Disease activity assessments:
 - SELENA SLEDAI
 - BILAG
 - Joint count
 - PGA
- Patient Assessments:
 - LupusPRO
 - Patient global assessment (PtGA)
- Laboratory assessments prior to dosing with study medication
 - **Local Laboratory** (at the participating site)
 - CBC with differential
 - Comprehensive chemistry, amylase, lipase
 - C3, C4
 - Urinalysis with micro
 - **Central Laboratory** (see **MOOP Appendix E** for processing, storage and shipping instructions)
 - anti-dsDNA and anti-DNA/DWEYS antibody titers,
 - antibodies to Sm, RNP, Ro, La, anticardiolipin antibodies: IgG, IgA, IgM
 - cytokine levels
 - interferon signature
 - CRP

Unscheduled visits: At screening all subjects will be given investigator contact information for 24 hour use in the event of an emergency. At each study visit, all subjects will be reminded to call study personnel and arrange for an “unscheduled” visit immediately if they feel ill in any way or experience or have concerns about their health. Subjects will be evaluated and appropriate interventions will be put into place at the discretion of the investigator. If there has been a change in disease activity and an unscheduled visit occurs more than 10 days after an evaluation for disease activity using the SELENA SLEDAI, an assessment of disease activity using the SELENA SLEDAI should be done including the appropriate tests required to complete the SELENA SLEDAI.

Visit Windows: The visits on Days 7 and 14 allow a one day window on either side. The visits on Days 28, 56 and 84 allow for a 3 day window on either side.

5.4.2 Endpoints:

1. Primary endpoint

The primary endpoint is a mechanistic endpoint: inhibition of anti-dsDNA binding. Inhibition of anti-dsDNA binding will be determined by assessment of: change in anti-ds DNA antibody titers from baseline to Day 56.

Blood obtained for the anti-dsDNA antibody titers on Day 1 before administration of nelfinavir and on Days 14, 28, 56 and 84 will be spun and the serum stored at -20 or -80 degrees at each site. Following completion of Day 56, all of the Central Laboratory samples obtained thus far for each subject (Days 1-56 inclusive) will be batched and sent to the central site at the FIMR.

Serum samples for anti-dsDNA antibodies from individual subjects on Days 1, 14, 28 and 56 will then be run simultaneously in the Core Laboratory in the North Shore/LIJ Health System using an enzyme immunoassay. This will allow for an ongoing statistical analysis of response so that the rules of the Simon Two Stage design can be applied. Mechanistic blood samples collected on Day 84 can all be frozen as individual subjects complete the study and all of these samples can then be batched at the participating sites and sent to the Coordinating Center at the FIMR at study completion.

[figure not shown]
2. Secondary endpoints

a) Safety

Safety will be evaluated by determining the frequency of adverse events and serious adverse events including measurements of hematology, clinical chemistry, lipid profile and urinalysis parameters over the course of the study from baseline to day 56. Safety will also be determined by assessment of disease activity. All adverse events will be mapped into their MedDRA preferred terms and assessed according to criteria established by the National Cancer Institute—Common Terminology Criteria version 4 [NCI-CTCAE].

The Simon Two-Stage trial is an open-label trial with no placebo arm. We felt justified in including no placebo arm for the following primary reasons: (i) nelfinavir is safe and well-tolerated in HIV patients, (ii) after excluding subjects taking contraindicated medications, we have no reason to think that those enrolled will be at increased risk for toxicity to nelfinavir, (iii) we are dosing at or below the recommended dose of nelfinavir in HIV patients, (iv) we have carefully pre-determined stopping rules for toxicity, and (v) as an added immediate safety precaution, we will enroll the first four subjects sequentially with a 2 wk observation delay prior to enrolling the next subject.

To identify immediate unexpected toxicity issues, the first 4 subjects will be enrolled sequentially and each will be observed for 2 weeks prior to enrolling the next subject (Fig. 6). In

all subjects, safety will be evaluated by the frequency of Adverse Events (AEs), serious AEs and changes in disease

activity over the course of the study from baseline to day 56 (see Protections for Human Subjects section for more complete safety). We envision AEs to include both NCI-CTCAE grades and worsening of a subject's SLE (*e.g.*, a new BILAG A on the BILAG index) (see section 8.1 for definitions of AE's, SAE's and lupus disease flares). Clearly, AEs of the same type that are considered to be related to study therapy will elicit appropriate caution from the Safety Officer. Additionally, all subjects will be given investigator contact information for 24 hour use and, at each study visit, will be reminded to call study personnel to arrange for an "unscheduled" visit if they have concerns about their health.

While the Safety Officer has ultimate authority to address safety, we have established pre-determined stopping/pausing rules, as defined by the number and type of AEs (Table 1). These stopping rules comprise three levels of surveillance:

Table 1	Stopping Rules – DSMB
1 st 4 subjects:	3 grade 3 or 4 AEs of same type 4 grade 3 or 4 AEs of any type
1 st 13 subjects:	4 grade 3 or 4 AEs of same type 5 grade 3 or 4 AEs of any type
All 43 subjects:	10 grade 3 or 4 AEs of same type 15 grade 3 or 4 AEs of any type

- (i) the first 4 subjects (Table 1, row 2)
- (ii) the entire Stage 1 (first 4 plus next 9 subjects, Table 1, row 3) and
- (iii) the overall trial (all 43 evaluable subjects, Table 1, row 4).

Enrollment will proceed only if these stopping rules have not been violated. In addition, protocol-specified requirements for the treatment of subjects will be discontinued for subjects under the following conditions: (i) at any time at the request of the subject, (ii) if the subject's health, safety, and/or well-being is threatened, (iii) if the subject requires an increase in dose of any concurrent SLE medications or experiences a grade 3 or higher NCI-CTCAE that is considered to be related to study therapy or (iv) if the subject becomes pregnant. Even though AE's may occur at any time in the 56 day treatment period, eligible subjects will continue to be enrolled regardless of how many subjects are still within the 56 day treatment and 28 day observation period. The rationale for this is that this is not a Phase I study and the study drug, nelfinavir, is FDA approved with a very good safety profile.

b) Disease activity

This study is exploratory and is not powered to adequately assess efficacy. However, we plan to enroll subjects with mild to moderate disease activity that, in the investigators opinion, will not require additional corticosteroids or immunosuppression for treatment of their disease activity. Five different assessments of disease activity are planned therefore we anticipate that we will be able to detect a trend for efficacy in those treated with nelfinavir. The potential effect of nelfinavir on clinical indicators of disease will be evaluated descriptively. Clinical indicators of disease will include:

- Changes in serum C3 and C4 complement levels from baseline to Day 56;
- Changes in serum CRP from baseline to Day 56;
- Changes in the SELENA SLEDAI score from baseline to Day 56;
- Changes in the PGA from baseline to Day 56;
- Changes in from baseline to Day 56;
- Changes in Joint Count from baseline to Day 56;
- Changes in BILAG scores from baseline to Day 56.

c) Health related quality of life

The potential effects of nelfinavir on patient quality of life will be assessed by changes in patient reported outcome measures from baseline to Day 56. The quality of life measures for this clinical trial include the following:

- The LupusPro Health Survey is a validated patient reported measure of functional health and well-being generalizable across ethnic backgrounds and gender [37].
- The patient global assessment scale is a 10 cm visual analogue scale with 1 mm increments from 0 through 100. 0 reflects no disease activity in the patient's assessment and 100 reflects maximum disease activity.

d) Interferon signature

Secondary analyses will explore the potential effect of nelfinavir on the expression of the IFN signature. Changes in expression of IFN inducible genes will be determined from baseline to Day 56. Expression of IFN inducible genes will be determined in two ways:

- Transfer of the IFN signature: as described previously [38], serum from SLE subjects will be incubated with normal PBMC and expression of IFN inducible genes will be measured using reverse transcriptase PCR.
- Microarray analysis: Expression of IFN inducible genes in peripheral blood will be measured by microarray analysis of RNA (extracted from whole blood in the PaxGene tubes) using the Illumina HT12v4 platform.

e) Cytokines

Changes in serum cytokine levels (IL-1, IL-6, and TNF α) from baseline to Day 56 will be determined for each treatment group at each dose level using ELISA assays in [name] laboratory.

f) Serology/Anticardiolipin Antibody Binding

Assessment of changes in autoantibody binding, including anti-Ro, La, Sm, RNP and cardiolipin antibodies, from baseline to Day 56 will be similar to the assessment of anti-dsDNA antibody binding. Investigators and study personnel will be blinded to autoantibody titers drawn during the course of the study. Blood obtained for the autoantibody titers will be spun and the serum stored at -20 or -80 degrees at each site on Days 1, 14, 28, 56 and 84. Frozen sera for the Central Laboratory for Days 1-56 will be sent overnight to the Coordinating Center following the Day 56 visit for each subject for determination of the primary endpoint. At study completion, all of the Day 84 Central Laboratory samples will be batched and sent to the Feinstein Institute. The samples will then be run simultaneously in the core laboratory in the North Shore/LIJ Health System.

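### For subjects who start within 10 days of screening, SELENA SLEDAI change runs from the eligibility score, with no stated analgesic hold, to a Day 56 score taken under the hold

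*Combined protocol and SAP*

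**What the plan says.** Section 5.4.1 describes screening as the visit that decides entry: "Consenting subjects will participate in a screening visit where assessments will be performed to establish eligibility". SELENA SLEDAI and BILAG are the disease activity measures taken there. Under Section 5.2, item 4, a subject needs at least 2 SLEDAI points without counting serology.

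The Day 1 text then splits subjects by timing. Those who "are returning for the Day 1 visit more than 10 days after the screening visit" have a new SELENA SLEDAI before dosing. For those who come back sooner, "the SELENA SLEDAI assessment obtained at screening should be used as the Day 1 SELENA SLEDAI", and SLEDAI is absent from their Day 1 list. Their physical exam, BILAG, joint count and PGA are still done that day.

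Section 5.3 says that NSAIDs and Tylenol "should be held overnight or for 12 hours prior to each assessment of disease activity on Days 1, 28, 56 and 84". The Day 56 text repeats this: "Subjects will be asked to refrain from taking Tylenol or NSAIDS and to fast after midnight the night prior to this visit". Neither Section 5.3 nor the screening text states a hold for screening.

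Section 5.4.2 b) lists among the clinical indicators "Changes in the SELENA SLEDAI score from baseline to Day 56", and says of the analysis: "The potential effect of nelfinavir on clinical indicators of disease will be evaluated descriptively". Section 7.1 and Section 7.1.1 make no distinction by baseline source.

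**The concern.** A change score is easiest to read when both ends are measured in the same way and the first end is not the measurement that admitted the subject. In the early-returning group neither condition is assured. The baseline is the qualifying score itself, so chance variation that helped a subject reach the threshold stays in the baseline. It may also have been taken with analgesics on board, whereas Day 56 is taken after they have been withheld. Subjects who return later have a separate Day 1 score under the hold. The interval between screening and Day 1 thus decides which kind of baseline a subject has.

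Two secondary objectives concern disease activity: that nelfinavir does not raise it, and that it lowers it. SLEDAI change is one of the measures bearing on them. With no placebo arm, nothing inside the trial shows how much of an observed SLEDAI change comes from the way the baseline was taken.

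**Working it through.** The plan states no figure on this point, so there is none to reproduce. The check sets the texts side by side and then asks what can be said about direction and size.

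**Step 1. The two groups compared (Sections 5.2, 5.3, 5.4.1)**

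| | Day 1 within 10 days | Day 1 after more than 10 days |
|---|---|---|
| Baseline SLEDAI | Screening score | New score on Day 1, before dosing |
| Same measurement as the screening score? | Yes | No |
| Hold stated for the visit that supplies it? | No | Yes |
| Hold stated for Day 56? | Yes | Yes |
| Exam, BILAG, joint count, PGA on Day 1? | Yes | Yes |

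Both features fall on the same subjects, the early returners. An early return looks feasible: Section 5.4.1 promises antibody results within 3 days of receipt, and Section 3.2 has drug shipped overnight.

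**Step 2. Direction**

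- A lower cut-off of 2 non-serologic points, with the same score reused as baseline, tends to produce an apparent fall later.
- Item 4 also caps activity: no active renal or nervous system disease and no BILAG A. Selection against high activity pulls the other way.
- If analgesics suppress a scored sign or symptom at screening and are withheld before Day 56, the later score could look worse. The documents do not show that a 12-hour hold moves SLEDAI, nor how many subjects use these drugs.

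These components can offset one another within a subject. The net sign is not determined.

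**Step 3. Size, illustration only**

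The documents give no mean, SD or test-retest correlation for SLEDAI, so every input here is assumed. Under a normal approximation with a single lower cut-off at 2, the expected fall with no drug effect is

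d = (1 − ρ) × SD × φ(c) / (1 − Φ(c)), with c = (2 − mean) / SD.

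- Mean 4, SD 3, ρ 0.7: c = −0.667, so d = 0.3 × 3 × 0.319 / 0.748 = 0.38 points.
- Smallest over the assumed range (mean 6, SD 2, ρ 0.9): c = −2, so d = 0.1 × 2 × 0.054 / 0.977 = 0.01.
- Largest (mean 2, SD 4, ρ 0.5): c = 0, so d = 0.5 × 4 × 0.399 / 0.5 = 1.6.

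Across means of 2 to 6, SDs of 2 to 4 and ρ of 0.5 to 0.9, d therefore runs from about 0.01 to 1.6 points per affected subject. The formula leaves out the cap on activity and the hold, so it describes one component and not the net bias.

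**Step 4. Share affected**

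If a fraction f of subjects return within 10 days, this component contributes f × d to the trial mean. The documents do not give f, so it lies between 0 and 1. At an assumed f of 0.5 and d of 0.38, it is 0.5 × 0.38 = 0.19 points.

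**The case against.** The best defence is that the rule is prespecified and appears deliberate. Section 5.4.1 uses the same 10-day interval at unscheduled visits before calling for another SLEDAI, so the protocol treats a score as current for that long and spares repeat laboratory work. This stands as an explanation for reusing laboratory results. It does not explain omitting the clinical items on a day when the exam, BILAG and joint count are done under the hold anyway.

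Several other points stand:

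- Item 4 of Section 5.2 names no time point, unlike items 5 and 6. If it must still be met on Day 1, the later returners' Day 1 score is selected too, and rescoring would not remove all selection.
- The entry threshold applies to the score without serology, while the endpoint is the SELENA SLEDAI score.
- That no hold is stated for screening does not mean analgesics were taken. The full Schedule of Events is in the manual of procedures, which is not among the documents.
- Lupus flare is defined through BILAG 2004 (Section 8.1), not SLEDAI.

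A reader might infer that the rule makes nelfinavir look better than it is, that the two groups carry opposing biases, or that both disease activity objectives are undermined. The documents support none of these. The cap on activity and the hold can work against an apparent improvement, both features sit in the same group, and SLEDAI is one of several indicators in a study that Section 5.4.2 describes as not powered for efficacy.

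**Conclusion.** The point holds as a minor inconsistency in measurement. For early returners, SLEDAI change to Day 56 starts from the eligibility score, possibly taken without the hold, and ends with a score under it; later returners have a separate baseline under the hold. The analysis section neither adjusts for this nor reports it.

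The net direction and size cannot be determined from the documents. The range in the working rests wholly on assumed values and is not evidence about this trial.

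The consequence is confined to one descriptive secondary measure. The primary endpoint uses a titer drawn on Day 1 before dosing, so the Simon decision is untouched, and BILAG, joint count and PGA have their own Day 1 baselines. It deserves correction because the trial has no control arm and the remedy costs almost nothing. The conclusion assumes that the manual of procedures adds no hold at screening and that some subjects do return within 10 days.

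**What to change.** In the Day 1 text of Section 5.4.1, have the clinical SLEDAI items scored on Day 1, under the hold already required for that visit, for every subject. Use that score as the baseline in Section 5.4.2 b). When Day 1 falls within 10 days of screening, carry forward only the laboratory items.

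Where Day 1 visits have already taken place under the present rule, report SLEDAI change to Day 56 separately by baseline source (carried forward or newly scored), with the number of subjects in each.

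The cost is a few minutes of scoring at a visit where the exam, BILAG and joint count are already done; no tests are added. The downside is that early returners' baseline would join Day 1 clinical items to laboratory items up to 10 days old, which should be stated when the results are reported.
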